Data Analysis Strategy. A series of multilevel longitudinal models were evaluated using SAS Proc Mixed to describe the change in number of Set 1 and Set 2 words accurately defined over seven test points: pre-treatment, 36 exposures in Treatment 1 (i.e., last Treatment 1 session), immediate post-Treatment 1, 2-week post-Treatment 1, 36 exposures in the second treatment (i.e., last Treatment 2 session), immediate post-Treatment 2, and 2-week post-Treatment 2. Because the number of exposures varied for the interim definition tests, only the 36-exposure interim definition test data, which was consistent for all treatment conditions, were used. We expected significant slopes for Set 1 words during Treatment 1 when they were the target of intervention. We had no hypotheses about whether Set 1 words would decline or would be maintained after Treatment 1 ended and monitoring continued during Treatment 2. We expected non-significant slopes for Set 2 words during Treatment 1, when those words were not the focus of intervention, and significant slopes for Set 2 words during Treatment 2 when they were the target of intervention. Because the number of words defined were counts, the natural log of the words defined was modeled resulting in a model equivalent to a generalized linear mixed model with a negative binomial link function.

The significance of fixed effects was evaluated using Wald tests, and the significance of random effects was evaluated using likelihood ratio tests and information criteria between models with the same fixed effects. We evaluated models with time coded as days since the start of intervention as well as categorically by intervention point. The categorical model fit the data better. The final categorical coding of time is shown in Table 7. Because there were two treatment phases (Treatment 1 vs. Treatment 2) with different expectations for change in Set 1 versus Set 2 words in each phase, we examined a piecewise model of change in which the change related to the first treatment phase (i.e., pre-treatment, 36 exposures in Treatment 1, immediate post-

Treatment 1) was described by one linear slope and change related to the second treatment phase (i.e., 2-week post-Treatment 1, 36 exposures in the second treatment, and immediate post-Treatment 2) was described by a second linear slope. This allows the slope for each word set to differ across each phase, as predicted.

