Results. Results are reported fully in Storkel, H. L., Komesidou, R., Pezold, M. J., Pitt, A. R., Fleming, K. J., & Romine, R. S. (2019). The impact of dose and dose frequency on word learning by kindergarten children with developmental language disorder during interactive book reading. *Language, Speech, and Hearing Services in Schools*, 50, 518–539. https://doi.org/10.1044/2019_LSHSS-VOIA-18-0131 - open access

Summary of Results. Results showed that children with DLD learned a significant number of words during treatment regardless of the dose and dose frequency format, but that significant forgetting of newly learned words occurred in all formats once treatment was withdrawn. Individual differences in word learning were related to CELF Core Language and CELF Understanding Spoken Paragraphs scores.

Conclusion. When administered at an adequate intensity, variation in the dose and dose frequency of interactive book reading does not appear to influence word learning by children with DLD. Although interactive book reading continues to show promise as an effective word learning intervention for children with DLD, further development is needed to enhance the effectiveness of this treatment approach.

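### Does the two-slope model leave the reported two-week forgetting without a test?

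*Combined protocol and SAP*

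**What the plan says.** The Data Analysis Strategy models the number of words defined, on the natural log scale, over seven test points. The list ends with "immediate post-Treatment 2, and 2-week post-Treatment 2". On the form of time it says: "We evaluated models with time coded as days since the start of intervention as well as categorically by intervention point". It adds that the categorical form fitted better and that "The final categorical coding of time is shown in Table 7".

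It then describes a piecewise model. One slope runs from the pre-treatment test through the last Treatment 1 session to the immediate post-test. The other is for "change related to the second treatment phase (i.e., 2-week post-Treatment 1, 36 exposures in the second treatment, and immediate post-Treatment 2". The stated reason is: "This allows the slope for each word set to differ across each phase, as predicted". For inference, "The significance of fixed effects was evaluated using Wald tests".

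On decline, the only statement is "We had no hypotheses about whether Set 1 words would decline or would be maintained after Treatment 1 ended". The Summary of Results nevertheless reports that "significant forgetting of newly learned words occurred in all formats once treatment was withdrawn". The definition task was given at two weeks after each treatment (Primary outcome measure), on all 60 words (Summary of the Design).

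**The concern.** The two slopes appear to leave out exactly the data that a statement about forgetting needs. The last test is the only delayed test of Set 2 words after their own treatment, and it belongs to no slope. For Set 1, the first two weeks after treatment lie between the end of one slope and the start of the other. The one decline estimate that the prose does describe is the Set 1 slope in the second phase. It starts at the two-week test, so it measures later decline across 5-12 weeks of Treatment 2.

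Slopes are said to vary by word set and phase, with no mention of dose, dose frequency or arm. If the prose were the whole model, one of the reported results, and its extension to every format, would have no identifiable test behind it.

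**Working it through.** **Count.** The points listed are: pre-treatment; last Treatment 1 session; immediate and two-week after Treatment 1; last Treatment 2 session; immediate and two-week after Treatment 2. That is 7. Slope 1 takes 3 and slope 2 takes 3, with none shared, so 6 are assigned. The one left over is the two-week test after Treatment 2.

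**What each reading of the time coding can test.** Over the seven points in order, code slope 1 as (0,1,2,2,2,2,2) and slope 2 as (0,0,0,0,1,2,2). A contrast is the difference between two rows of the design.

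| Reading | Immediate to two-week, Treatment 1 | Immediate to two-week, Treatment 2 | Two-week Treatment 1 to immediate Treatment 2 |
|---|---|---|---|
| A. Two slopes, level carried forward | 0 by construction | 0 by construction | 2 × slope 2 |
| B. A plus a shift at the start of phase 2 | the shift | 0 by construction | 2 × slope 2 |
| C. Slope 2 starting from the immediate test, (0,0,0,1,2,3,3) | 1 × slope 2, not separate | 0 by construction | 2 × slope 2 |
| D. B plus a drop at the last test | the shift | the drop | 2 × slope 2 |
| E. One category per occasion | free | free | free |

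Under A and C neither two-week loss has its own test. Under B only the first does. Under D and E both do. Reading D has 5 time parameters. They remain estimable for each word set after removing the interim test given during the other set's treatment, because the Summary of the Design describes interim testing only for the set under treatment.

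**Which reading applies.** The prose on the slopes suggests A, B or C. The sentence on coding by intervention point suggests E, and Table 7 could show D. The document defers to that table, so the prose alone cannot decide between them.

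**Would adding a term to the slopes clearly be better?** Not necessarily. Take assumed Set 1 counts of 1, 4, 7 in phase 1, then 7 at two weeks, so no loss in that interval. On the log scale the least-squares line through the first three points ends at (ln 1 + ln 4 + ln 7)/3 + (ln 7 − ln 1)/2 = (0 + 1.386 + 1.946)/3 + 0.973 = 2.084. A retention term measured from that line is 1.946 − 2.084 = −0.138. That is an apparent loss of 1 − e^(−0.138) = 13% where there was none. The occasion contrast gives ln 7 − ln 7 = 0. The direct comparison of the two tests is therefore the natural estimate, and it is the one that coding by intervention point provides.

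**The case for a change.** The strongest case for a change is that, even with occasion-level coding, someone must name the contrast and its interaction with format. The two-week tests belong to the primary outcome schedule, so this is not a side measure. A significant overall loss also does not establish loss in each format. With k independent, equally precise formats, the per-format z is the overall z divided by √k. An assumed overall z of 3 becomes 2.12 for k = 2 (3/1.414) and 1.50 for k = 4 (3/2), and the latter is below 1.96.

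Part of this stands. From this document alone a reader cannot trace which estimate lies behind the forgetting statement, whether it covers Set 2, or how it was tested by format. The per-format arithmetic, however, describes a hypothetical trial: the document gives no sample size, standard error or z, and k is assumed. The statement also sits in a short summary that sends the reader to a publication for full results. The tracing question belongs there and in Table 7.

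**Conclusion.** No change to the plan. The description is incomplete by one test point of seven and by two unnamed contrasts, but the documents do not show that the analysis lacked them. Three things support this.

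- The data exist: all 60 words were tested at both delayed occasions.
- The text states a time coding under which the immediate-to-two-week contrasts follow directly, and it places the detail in a table not available here.
- Forgetting is neither in the Purpose nor the subject of a stated hypothesis, so the result reads as exploratory, and a short summary need not carry every contrast.

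The omitted point comes after treatment ends, so leaving it out of slopes meant to describe change during treatment is reasonable. The learning result is not shown to be biased.

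This rests on Table 7 or the full report containing the retention comparison, which cannot be confirmed here. If neither did, the phrase about all formats would be unsupported; that would be a fault in reporting the result, and the design and data collection would still be sound.
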